#### 13.4 Safety evaluation

Data from all subjects who receive any drug while on study will be included in the safety analyses. Subjects enrolled on to the study but who did not take any study drugs, will not be evaluated for safety.

The severity of the toxicities will be graded according to the NCI CTCAE v4.0 whenever possible (Appendix C).

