**STUDY DESIGN:**

This is an open label, phase II, single arm, and single institution study investigating daily alternating therapy with the IMiD™ compounds, thalidomide and lenalidomide, plus rituximab in untreated CLL patients requiring treatment. In order to obtain correlative samples, patients will receive a two week course of single agent thalidomide or lenalidomide before beginning treatment with the combination regimen. Half of the patients (odd numbered subjects) will start with a two week course of single agent thalidomide and the other half of the patients (even numbered subjects) will start with a two week course of single agent lenalidomide. This will allow the study of correlative samples of monotherapy with either IMiD™ agent. In Cycle -1, half of the patients (odd numbered subjects) will receive thalidomide 50mg PO daily on days 1-14, followed by no treatment days 15-28. The other half of the patients (even numbered subjects) will receive lenalidomide PO daily on days 1-14, followed by no treatment days 15-28. Starting cycle 1, patients will receive thalidomide 50 mg every other day (every odd day on days 1-28: Days 1, 3, 5, 7, 9, 11, 13, 15, 17, 19, 21, 23, 25 & 27 of a 28 day cycle) alternating with lenalidomide on alternate every other day, dosed based upon current level with stepwise incremental dosing (every even day on days 1-28: Days 2, 4, 6, 8, 10, 12, 14, 16, 18, 20, 22, 24, 26 & 28 of a 28 day cycle). The starting dose of lenalidomide will be based on calculated creatinine clearance and the dose of lenalidomide may be escalated as tolerated to maximal dose of 25 mg (see Section 5 for details). Rituximab 375 mg/m^2 will be administered on days 1, 8, 15 and 22 starting with Cycle 1 and then again on the same weekly x 4 schedule every 6th cycle through Cycle 19 (Cycles 7, 13, and 19).

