**STUDY DURATION:** 3 years**TOTAL SAMPLE SIZE:** 24 patients**DOSING REGIMEN(S):**

**Cycle -1:** thalidomide 50 mg PO daily on days 1-14 or lenalidomide PO daily on days 1-14 of a 28 day cycle (odd numbered subjects will receive thalidomide and even numbered subjects will receive lenalidomide). Days 15-28 no drug treatment.

**Starting on Cycle 1:** Alternating every other day thalidomide 50 mg (every ODD day on days 1-28: Days-1,3,5,7,9,11,13,15,17,19,21,23,25 & 27 of a 28 day cycle) with lenalidomide (every EVEN day on days 1-28: Days-

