### **1.2. Secondary Objectives**

- To determine the safety, tolerability, and feasibility of combining thalidomide, lenalidomide, and rituximab as initial treatment for patients with CLL requiring therapy.
- To evaluate duration of response, time to response, progression free survival and overall survival
- To perform correlative studies to determine the potential mechanism of action of how thalidomide and lenalidomide are affecting CLL lymphocytes.

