#### **5. TREATMENT PLAN**

##### **5.1 Overall design**

This is an open label, phase II, single arm, and single institution study investigating daily alternating IMiD™ agent therapy with thalidomide and lenalidomide plus rituximab in untreated CLL patients requiring treatment as outlined in the IWCLL update of the 1996 NCI-Working Group criteria for CLL [15]. Half of the patients (odd numbered subjects) will start with a two week course of single agent thalidomide and the other half of the patients (even numbered subjects) will start with a two week course of single agent lenalidomide in order to perform correlative studies to elucidate the

mechanisms of action of thalidomide and lenalidomide. Daily alternating IMiD™ agent therapy will begin with cycle 2 as follows:

- Cycle -1: half of the patients (odd numbered subjects) will receive thalidomide 50 mg PO daily on days 1-14, followed by no treatment days 15-28 and the other half of the patients (even numbered subjects) will receive lenalidomide PO daily on days 1-14, followed by no treatment days 15-28. The lenalidomide dose will be based on baseline calculated creatinine clearance\*.
- Cycles 1 and all escalation cycles: Patients will receive thalidomide 50 mg (every **ODD** day on Days 1-28 of a 28 day cycle: Days 1, 3, 5, 7, 9, 11, 13, 15, 17, 19, 21, 23, 25 & 27) with lenalidomide (every **EVEN** day on Days 1-28 of a 28 day cycle: Days 2, 4, 6, 8, 10, 12, 14, 16, 18, 20, 22, 24, 26 & 28). Each cycle will be 28 days in length. Patients who received lenalidomide during Cycle -1 will receive the same dose of lenalidomide starting with Cycle 1. For patients who did not receive lenalidomide during Cycle -1, lenalidomide will be initiated at a starting dose based on baseline calculated creatinine clearance\*.
- Cycle 1: Patients will also receive rituximab 375 mg/m^2 IV on Days 1, 8, 15 and 22 (+/- 2 days) and then again on the same weekly x 4 schedule every 6th cycle through Cycle 19 (Cycle 7, 13, and 19).

\*\*\*\* Rituximab can be given +/- 2days.

\*\*\*\*All correlative work must be drawn prior to Rituximab administration regardless of the day Rituximab is given.

\*The lenalidomide starting dose will be based on baseline calculated creatinine clearance as follows:

Lenalidomide Starting Dose Based on Renal Function at Study Entry	
Baseline Calculated Creatinine Clearance (by Cockcroft-Gault)	Starting Lenalidomide Dose

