### 13.3 Statistical Methodology

Primary Endpoint:

- The primary endpoint of response rate (overall, CR, PR) will be estimated and a 95% confidence interval will be estimated via binomial proportions

Secondary Endpoints:

- With adequate follow-up time, progression-free survival (PFS) will be assessed by Kaplan-Meier survival analysis and 95% confidence intervals will be calculated using Greenwood's formulae. PFS will be defined as the time from the first treatment day until objective or symptomatic progression (or until date of last follow-up if no progression).
- Duration of Response: from the end of the last treatment until evidence of progressive disease.
- Time to Response
- Overall Survival
- The frequency of subjects experiencing toxicities will be tabulated. Toxicities will be assessed and graded according to CTCAE v4.0 terminology. Exact 95% confidence intervals around the toxicity proportions will be calculated to assess the precision of the obtained estimates.

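### The planned toxicity tables do not separate the single-agent lead-in (Cycle -1) from the three-drug regimen, so the reported rates describe the whole protocol sequence and not specifically the combination

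*Combined protocol and SAP*

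**What the plan says.** The secondary objective in Section 1.2 is "To determine the safety, tolerability, and feasibility of combining thalidomide, lenalidomide, and rituximab as initial treatment for patients with CLL requiring therapy".

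The combination is not what patients receive first. Under the Schema's study design, "patients will receive a two week course of single agent thalidomide or lenalidomide before beginning treatment with the combination regimen", in order to obtain correlative samples. The dosing summary gives this Cycle -1 as "thalidomide 50 mg PO daily on days 1-14 or lenalidomide PO daily on days 1-14 of a 28 day cycle", with the drug set by odd or even subject number. Days 15 to 28 are drug-free. Rituximab is given on "days 1, 8, 15 and 22 starting with Cycle 1", so nobody receives it in the lead-in.

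For the analysis, Section 13.3 says "The frequency of subjects experiencing toxicities will be tabulated" and adds "Exact 95% confidence intervals around the toxicity proportions will be calculated to assess the precision of the obtained estimates". Section 13.4 sets the population: "Data from all subjects who receive any drug while on study will be included in the safety analyses". The study calendar in Section 10 has adverse events recorded from Cycle -1. Section 13 has no split by period or by lead-in drug, and defines no set of patients who started the combination.

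**The concern.** The objective asks about three drugs given together. The only planned summary is a per-patient frequency over everyone who took any drug. Two kinds of patient separate that summary from the target:

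- A patient whose only occurrence of a toxicity was under single-agent dosing in Cycle -1 counts in the numerator.
- A patient who leaves during Cycle -1 counts in the denominator without having received the combination.

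Both can happen. Section 5.5.1 says tumor lysis syndrome (TLS) risk is highest in the first cycle of therapy, and patients assigned lenalidomide first meet that drug in Cycle -1. Intolerance of either oral drug (Section 5.4.1), stopping either for any reason (Section 5.6), inability to take allopurinol through the first two cycles (Section 5.5.1) and grade 4 or blistering rash (Table 2) all end participation and can occur before Cycle 1.

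A reader of the final report could take a toxicity rate as the rate on the combination when it partly reflects single-agent treatment. These summaries also inform the monitoring board, which may stop the study (Section 12.3).

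**Working it through.** **The plan's own figure.** No sample size is stated for safety; the denominator comes from the Simon minimax design in Section 13.1. Exact enumeration reproduces that design: 11 then 24 patients, boundaries 6/11 and 17/24, attained alpha 0.0930 and power 0.8015. The sizing is not in question. N = 24 below assumes that the second stage is completed.

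**Period boundary.** The Schema, Section 5.2 and the Section 5.1 bullets start the combination in Cycle 1. One introductory sentence in Section 5.1 says cycle 2. I use Cycle 1; the sentence should be reconciled, because a table by period needs one boundary.

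**Formulas.** For a given toxicity, let
- c = patients with it on the combination,
- m = patients with it only in Cycle -1,
- k = treated patients who never start Cycle 1.

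As planned: (c + m) / 24. Among patients who start the combination: c / (24 - k).

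The difference is [24m - k(c + m)] / [24(24 - k)]. It is zero when m = 0 and k = 0, and otherwise only by coincidence. For example, c = 6, m = 2, k = 6 gives 8/24 and 6/18, both 33.3%.

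**Numbers.** The documents give no value for c, m or k, so these are assumptions, with c = 6 throughout. Intervals are exact (Clopper-Pearson) 95%.

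| m | k | As planned | From Cycle 1, among starters | Difference (points) |
|---|---|---|---|---|
| 0 | 0 | 6/24 = 25.0% (9.8-46.7) | 6/24 = 25.0% (9.8-46.7) | 0 |
| 2 | 0 | 8/24 = 33.3% (15.6-55.3) | 6/24 = 25.0% (9.8-46.7) | +8.3 |
| 3 | 0 | 9/24 = 37.5% (18.8-59.4) | 6/24 = 25.0% (9.8-46.7) | +12.5 |
| 4 | 0 | 10/24 = 41.7% (22.1-63.4) | 6/24 = 25.0% (9.8-46.7) | +16.7 |
| 2 | 2 | 8/24 = 33.3% (15.6-55.3) | 6/22 = 27.3% (10.7-50.2) | +6.1 |
| 0 | 2 | 6/24 = 25.0% (9.8-46.7) | 6/22 = 27.3% (10.7-50.2) | -2.3 |
| 0 | 4 | 6/24 = 25.0% (9.8-46.7) | 6/20 = 30.0% (11.9-54.3) | -5.0 |

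The gap can run either way. The interval for 6/24 is itself 46.7 - 9.8 = 36.9 points wide, so the denominator effect alone is small beside sampling error.

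**Thalidomide exposure in the two periods.** In Cycle -1, odd-numbered subjects "will receive thalidomide 50 mg PO daily on days 1-14, followed by no treatment days 15-28": 14 x 50 = 700 mg per 28 days. From Cycle 1 the drug is taken on the 14 odd days: again 14 x 50 = 700 mg. Over days 1 to 14 alone it is 14 doses (700 mg) against 7 doses (350 mg). The pace differs; the cycle total does not.

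**Precision of a lead-in table.** With about 12 patients per drug, 0/12 has an exact upper limit of 26.5%.

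**The case against.** The strongest reply is that nothing in the plan is wrong. An all-treated safety set is standard, and a rate over it is a valid summary of the sequence patients actually went through. Section 13.3 does not say there will be only one table, and the data for a split are collected: adverse events are recorded in Cycle -1, and Section 7.3.2 asks for the duration and intensity of each episode. Toxicity is a secondary endpoint, and no stopping boundary or go/no-go rule uses these proportions. All of this stands. It does not supply a planned analysis aimed at the combination.

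Three stronger readings are tempting, and the documents do not support them.

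- *The planned rate is biased, and a figure such as 6/22 is the correct one.* The rate among Cycle 1 starters is conditional on coming through the lead-in. It leaves out the least tolerant patients and can understate first-exposure risk. Patients who leave in Cycle -1 also bear on tolerability and feasibility, which the same objective names. The two rates answer different questions.
- *The plan throws away a single-agent comparison.* Nothing is discarded. The lead-in was designed for correlative sampling, assignment follows subject number, and with about 12 patients per drug the comparison can only be descriptive.
- *Lead-in thalidomide exposure is double that of the combination.* This holds only within the two dosing weeks; the 28-day total is equal.

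**Conclusion.** The point holds as a gap in the planned safety reporting. As written, Sections 13.3 and 13.4 yield a rate for the whole protocol sequence and none specific to the three-drug regimen.

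The size and direction of the difference cannot be known from the documents. The range of -5.0 to +16.7 points rests wholly on assumed counts (c = 6; m and k each from 0 to 4) and on all 24 patients being treated. For toxicities that appear after months of treatment the difference may be nil, because combination exposure is much longer than 14 dosing days. It matters most for early events. TLS is the clearest case: first lenalidomide exposure falls in Cycle -1 for half the patients and in Cycle 1, together with rituximab, for the other half.

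The primary response analysis is unaffected. This is a low-cost improvement worth making, not a flaw that undermines the trial.

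**What to change.** Keep the all-treated table and add to Sections 13.3/13.4 toxicity tables by period, with exact 95% intervals:

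- (a) Cycle -1, by lead-in drug, labelled descriptive only (about 12 patients each).
- (b) Events that start, or worsen in grade, from the first Cycle 1 dose, among patients who start Cycle 1.

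Report how many patients leave during Cycle -1 and why. State that (b) is conditional on coming through the lead-in, so it is read beside the all-treated table and does not replace it. The start-or-worsen rule settles how to count an event that begins in Cycle -1 and persists into Cycle 1.

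The cost is a few sentences, one extra table and a slightly smaller denominator for (b). The adverse event log must show the onset date and the date of any worsening in grade; the 14 drug-free days before Cycle 1 make assignment to a period practical. Specifying this in advance also avoids choosing the presentation after the data are seen.

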#### 13.5 Interim analyses

##### 13.5.1 Interim analysis strategy

Accrual will not be put on hold during the study in order to perform an interim analysis given the preliminary clinical data already generated demonstrating activity for lenalidomide in CLL. Efficacy and safety data will be analyzed after the first eleven patients reach cycle four. Data will be analyzed subsequently every four months in order to allow for assessments of response and toxicities. For the purpose of performing the interim analysis, responses will be assessed starting after cycle #6 of treatment and then every cycle thereafter.

In the first stage, 11 patients will enter the study. If 6 or fewer patients respond, the study will be terminated early and declared to have a negative result. If 7 or more patients respond, enrollment will be extended to 24 patients.

## **Appendix A: Risks of Fetal Exposure, Pregnancy Testing Guidelines and Acceptable Birth Control Methods**

## **Risks Associated with Pregnancy**

Lenalidomide is structurally related to thalidomide. Thalidomide is a known human teratogenic active substance that causes severe life-threatening birth defects. An embryofetal development study in animals indicates that lenalidomide produced malformations in the offspring of female monkeys who received the drug during pregnancy. The teratogenic effect of lenalidomide in humans cannot be ruled out. Therefore, a risk minimization plan to prevent pregnancy must be observed.

All study participants must be registered into the mandatory RevAssist® and S.T.E.P.S programs, and be willing and able to comply with the requirements of RevAssist® and S.T.E.P.S.

### Criteria for females of childbearing potential (FCBP)

This protocol defines a female of childbearing potential as a sexually mature woman who: 1) has not undergone a hysterectomy or bilateral oophorectomy or 2) has not been naturally postmenopausal (amenorrhea following cancer therapy does not rule out childbearing potential) for at least 24 consecutive months (i.e., has had menses at any time in the preceding 24 consecutive months).

### Counseling

For a female of childbearing potential, lenalidomide and thalidomide is contraindicated unless all of the following are met (i.e., all females of childbearing potential must be counseled concerning the following risks and requirements prior to the start of lenalidomide study therapy):

- She understands the potential teratogenic risk to the unborn child
- She understands the need for effective contraception, without interruption, 4 weeks before starting study treatment, throughout the entire duration of study treatment, dose interruption and 28 days after the end of study treatment
- She should be capable of complying with effective contraceptive measures
- She is informed and understands the potential consequences of pregnancy and the need to notify her study doctor immediately if there is a risk of pregnancy
- She understands the need to commence the study treatment as soon as study drug is dispensed following a negative pregnancy test
- She understands the need and accepts to undergo pregnancy testing based on the frequency outlined in this protocol

- She acknowledges that she understands the hazards and necessary precautions associated with the use of lenalidomide and thalidomide

The investigator must ensure that for females of childbearing potential:

- Complies with the conditions for pregnancy risk minimization, including confirmation that she has an adequate level of understanding
- Acknowledge the aforementioned requirements

For a female NOT of childbearing potential, lenalidomide and/or thalidomide is contraindicated unless all of the following are met (i.e., all females NOT of childbearing potential must be counseled concerning the following risks and requirements prior to the start of lenalidomide and/or thalidomide study therapy):

- She acknowledges that she understands the hazards and necessary precautions associated with the use of lenalidomide and/or thalidomide

Traces of lenalidomide have been found in semen. Male patients taking lenalidomide must meet the following conditions (i.e., all males must be counseled concerning the following risks and requirements prior to the start of lenalidomide and/or thalidomide study therapy):

- Understand the potential teratogenic risk if engaged in sexual activity with a pregnant female or a female of childbearing potential
- Understand the need for the use of a condom even if he has had a vasectomy, if engaged in sexual activity with a pregnant female or a female of childbearing potential.

### Contraception

Females of childbearing potential (FCBP) enrolled in this protocol must agree to use two reliable forms of contraception simultaneously or to practice complete abstinence from heterosexual contact during the following time periods related to this study: 1) for at least 28 days before starting study drug; 2) while participating in the study; 3) dose interruptions; and 4) for at least 28 days after study treatment discontinuation.

The two methods of reliable contraception must include one highly effective method and one additional effective (barrier) method. FCBP must be referred to a qualified provider of contraceptive methods if needed. The following are examples of highly effective and additional effective methods of contraception:

- Highly effective methods:
  - Intrauterine device (IUD)
  - Hormonal (birth control pills, injections, implants)

- Tubal ligation
- Partner’s vasectomy
- Additional effective methods:
  - Male condom
  - Diaphragm
  - Cervical Cap

Implants and levonorgestrel-releasing intrauterine systems are associated with an increased risk of infection at the time of insertion and irregular vaginal bleeding. Prophylactic antibiotics should be considered particularly in patients with neutropenia.

### Pregnancy testing

Medically supervised pregnancy tests with a minimum sensitivity of 25 mIU/mL must be performed for females of childbearing potential, including females of childbearing potential who commit to complete abstinence, as outlined below.

### **Before starting study drug**

#### *Female Patients:*

FCBP must have two negative pregnancy tests (sensitivity of at least 25 mIU/mL) prior to starting study drug. The first pregnancy test must be performed within 10 to 14 days prior to the start of study drug and the second pregnancy test must be performed within 24 hours prior to the start of study drug. The patient may not receive study drug until the study doctor has verified that the results of these pregnancy tests are negative.

#### *Male Patients:*

Must practice complete abstinence or agree to use a condom during sexual contact with a pregnant female or a female of childbearing potential while participating in the study, during dose interruptions and for at least 28 days following study drug discontinuation, even if he has undergone a successful vasectomy.

### **During study participation and for 28 days following study drug discontinuation**

#### *Female Patients:*

- FCBP with regular or no menstrual cycles must agree to have pregnancy tests weekly for the first 28 days of study participation and then every 28 days while on study, at study discontinuation, and at day 28 following study drug discontinuation. If menstrual cycles are irregular, the pregnancy testing must occur weekly for the first 28 days and

then every 14 days while on study, at study discontinuation, and at days 14 and 28 following study drug discontinuation.

- At each visit, the Investigator must confirm with the FCBP that she is continuing to use two reliable methods of birth control.
- Counseling about pregnancy precautions and the potential risks of fetal exposure must be conducted at a minimum of every 28 days.
- If pregnancy or a positive pregnancy test does occur in a study patient, study drug must be immediately discontinued.
- Pregnancy testing and counseling must be performed if a patient misses her period or if her pregnancy test or her menstrual bleeding is abnormal. Study drug treatment must be discontinued during this evaluation.
- Females must agree to abstain from breastfeeding during study participation and for at least 28 days after study drug discontinuation.

#### Male Patients:

- Counseling about the requirement for complete abstinence or condom use during sexual contact with a pregnant female or a female of childbearing potential and the potential risks of fetal exposure to lenalidomide must be conducted at a minimum of every 28 days.
- If pregnancy or a positive pregnancy test does occur in the partner of a male study patient during study participation, the investigator must be notified immediately.

